17.3. Analysis Populations

All analyses and data summaries will be conducted on the intention-to-treat (ITT) population which is defined as all participants registered regardless of non-compliance with the protocol or withdrawal from the study.

17.3.1 Frequency of Analyses

No formal analyses are planned until after the trial is closed to recruitment and the required number of patients have been registered. Final analysis of the feasibility study will be carried out when all available outcome data has been received, no earlier than 6 months after the close of recruitment.

17.3.2 Outcome Analysis

Analysis will report descriptive statistics and confidence interval (CI) estimates rather than hypothesis testing. Estimates will be obtained for data relating to outcomes (section 13) and progression criteria (Section 15.1).

Recruitment methods, uptake and follow-up

The feasibility and success of the recruitment strategy will be evaluated by summarising the screening, eligibility, consent and registration processes, including numbers of participants involved during each stage. Reasons for non-participation in the study will be summarised. Participant retention during follow-up, including number of participants completing/withdrawing from the study and reasons for withdrawal will be presented by therapeutic modality. Characteristics of participants lost to follow-up will be compared to those completing the study.

Intervention delivery and acceptability

Delivery of intervention by allocated therapist will be summarised as will cross over of therapist. Retention rate in the intervention will be evaluated by summarising the proportion of patients successfully completing the required amount of therapy, the number of early dropouts and reasons for drop-out, overall and by therapeutic modality. The methods for measuring adherence and fidelity to the intervention will be agreed and summarised including the number of therapy sessions attended/missed, evidence of delivery of key intervention components, supervision, and fidelity to self-harm approach and individual psychological therapy, by both the participant and therapist. The range of treatment-as-usual available and taken up by participants in addition to the trial intervention will be summarised.

Follow-up data collection

The feasibility and success of obtaining the self-reported self-harm data monthly via text message will be assessed by summarising the proportion of participants with available repetition of self-harm data monthly up to 6 months post-randomisation, and compared to self-harm data obtained through hospital records and self-report at 6 month follow-up. The feasibility and best method of obtaining self-reported six month outcome data will be assessed by summarising the proportion of participant's with available data by method of obtainment. Acceptability of questionnaires will be assessed by summarising overall and item level completion rates, time spent on questionnaires, and participants reported acceptability.

Statistical outcomes

To check our assumptions for the sample size for the definitive trial, we will assess the variability (standard deviation) of the self-reported outcomes at baseline and 6 months post-randomisation, and report summary statistics and 95% confidence intervals. For the primary outcome of the full trial, the CORE-OM, we will report change from baseline (with 95% confidence intervals), and the proportion of participants with reliable and clinically significant improvement (RCSI). An investigation of the clustering effect (ICC) relating to the therapists will be carried out and reported for the CORE-OM at 6 months with 95% confidence interval. Descriptive summaries will be used to explore self-reported outcomes at 6 months post-randomisation by method of intervention delivery (face-to-face, telephone or video call).

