12. ASSESSMENTS/DATA COLLECTION

Participating site teams will be expected to maintain a file of essential trial documentation (Investigator Site File) which will be provided by CTRU, and to keep copies of all completed case report forms (CRFs) for the trial, except questionnaires which will be sent to CTRU and stored centrally.

Participant assessments will take place at:

- Baseline (prior to registration) for complete measures
- Monthly post-registration up to 6-months for self-reported self-harm episodes via text message follow-up
- 6-months post-registration for complete measures via postal/questionnaire, supplemented by a maximum of two reminders and phone, video call or face-to-face interviews to maximise follow-up rates. Follow-up at 6 months will therefore correspond with the expected completion of the participant's therapy sessions, including any booster sessions.

Required data, assessment tools, collection time points and processes are described in detail in sections 12.1 to 12.5. This is summarized in table 1 below. A window of up to two weeks prior to registration will be recommended for baseline data (ideally baseline and registration will occur on the same day) and plus or minus two weeks from the target of 6 months post- registration for outcome data. The feasibility of these windows will be recorded.

Table 1: Summary of Assessments

Assessment (including who is involved)

Timeline (months post-randomisation)

	Baseline	monthly	6 months
Eligibility and consent			
- Eligibility assessment (inclusion criteria assessed by			
clinician, exclusion criteria assessed by Researcher)	Х		
- Consent (R)	Х		
Background and Demographics (P and R)			
- NHS number	Х		
- GP details	Х		
- Participant's contact details	Х		
- Education and employment	Х		
- Date of index event	Х		
- Details of 'index' event	Х		
- Date of hospital attendance / contact with services	Х		
- Self-harm history	Х		
- Current co-morbid physical / mental health	Х		
- Social and medical history	Х		
- Current psychotropic medications	Х		
- Source of referral	Х		
Follow-up data (P, R and T)			
- Therapy details including method of delivery	X		
- Therapist details including gender, age,			
qualifications and experience		Х	
- Therapist training details including competency			
assessment		Х	
- Therapist supervision details (supervisor)			Х
- Referrals to and attendance at other services			Х
- Medication details			Х
- Admissions to / attendance at hospital relating to			
self-harm			х

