12.3. Follow-Up Data

Participant-completed data

Questionnaires will be completed at 6 months post-registration via postal follow-up. Participants will be alerted to questionnaires being posted via text, and a maximum of two reminders will be sent to the participant. The Researcher may also telephone or video call the participant in an attempt to obtain the data if necessary. If the Researcher speaks to the participant and they do not wish to provide this, then this data will not be chased further.

The following data will be collected at 6 months:

- Clinical Outcomes in Routine Evaluation Outcome Measure (CORE-OM)
- Hopelessness Beck Hopelessness Scale
- Depression PHQ-9
- Social connectedness -The Social Connectedness Scale-Revised
- Self-reported episodes of self-harm
- Self-reported resource use primary and community care and medications and private financial burden due to self-harm (trial-specific).

Text messages

Text messages will be sent to the participant monthly to record occurrence of self-harm. The responses will not be routinely fed back to therapists, as they will be seeing clients weekly, and will be discussing self-harm issues on a regular basis with their clients. Separate consent will be sought for the texts and there will be an option for the participants to stop the messages by texting STOP. No free text responses will be possible. A contact telephone number and email address will be provided to allow respondents to raise questions with the research team if they wish.

Clinical data:

Data will be recorded on hospital attendances (including number and details of attendance / admission).

Therapy details will be collected from the therapist, and will include: therapy details (type, session offered and attended, dates, contact between sessions, method of delivery); therapy supervision details; referrals / attendance at other services; therapy content; repeat of self-harm, and medication details.

Therapist data:

Details on each therapist will be recorded and will include gender, age, qualifications and experience. Training data will also be recorded for each therapist, and will include the date and competency assessment. Supervision data will be recorded, and will include dates and details of each session.

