15. OUTCOMES

The outcomes relate to intervention delivery, acceptability and feasibility of recruitment, follow-up and outcome data collection, as follows :

Intervention delivery and acceptability

- Number and proportion of therapists undergoing training and deemed competent.
- Therapy delivery by randomly allocated therapist, cross over of patients to therapists.
- Proportion of participants attending therapy, completing the required number of therapy sessions, number of early drop-outs from treatment, reasons for early drop outs, overall and by therapy type (BT, ACT, PIT).
- Availability and uptake of other treatments and services accessed by participants
- Proportion of participants taking up telephone "top up" contact at end of therapy.
- Proportion of participants and therapists delivering key intervention components, overall and by therapy type (BT, ACT, PIT) as recorded by the therapist
- Proportion of treatment sessions by method of delivery
- Participant and therapist fidelity to the intervention including fidelity to the self-harm modifications and to the individual psychological therapeutic approach overall and by therapy type (BT, ACT, PIT) as recorded by the researcher rated audio-recordings.
- Number and attendance of therapy specific supervision sessions.

Recruitment methods, uptake and follow-up

- Number of patients screened for eligibility, overall and by site
- Number of study cards given out and proportion completed, overall and by site
- Method of referral e.g. Emergency Department, self-harm team, clinical staff, general practice.
- Proportion of patients who complete the study card, who could be followed-up by the Researcher to assess eligibility and proportion of those found eligible for the study, overall and by site
- Proportion of patients that consent and are registered to the study out of those found eligible
- Reasons for non-participation, overall and by site
- Proportion of patients completing the study out of those registered, number of withdrawals from follow-up data collection, reasons for withdrawal, overall and by site
- Number of losses to follow-up and characteristics of participants lost to follow-up

Follow-up data collection

- Proportion of participants with available monthly self-reported repetition of self-harm data
- Proportion of participants with 6 month self-reported outcome data, proportion obtained through postal, online, telephone or face to face administration

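### Share of 6-month data by collection route cannot identify a best method when post goes to everyone first and calls only supplement it (minor)

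*Protocol*

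**What the plan says.** Protocol section 17.3.2 sets the aim and the measure in one sentence. The aim is: "The feasibility and best method of obtaining self-reported six month outcome data will be assessed". The measure is the proportion of participants "with available data by method of obtainment". Section 15 lists the matching outcome as the proportion of participants with 6-month self-reported data, with the "proportion obtained through postal, online, telephone or face to face administration". Neither place gives, as a denominator, the number of people on whom each route was tried. Section 17.3 bases all summaries on all registered participants.

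The conduct sections describe an order of contact. Section 12.3 begins: "Questionnaires will be completed at 6 months post-registration via postal follow-up". It continues: "Participants will be alerted to questionnaires being posted via text, and a maximum of two reminders will be sent to the participant". Then: "The Researcher may also telephone or video call the participant in an attempt to obtain the data if necessary". Section 12 says the same of the 6-month assessment, describing post as "supplemented by a maximum of two reminders and phone, video call or face-to-face interviews to maximise follow-up rates". Table 1 gives postal administration by the trials unit at 6 months. Participants are randomised to therapy and therapist (section 10.5). No section assigns them to a method of data collection.

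Other places are looser. The flow chart in section 3 lists post, telephone and video call as alternatives. Sections 7.2 and 8 put online beside post, with telephone if appropriate. Section 15 lists online but not video call. Online has no described step in section 12, Table 1 or section 12.3.

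**The concern.** A share by route would compare methods fairly only if each route had the same chance of being used on the same kind of participant. Under sections 12 and 12.3 that is not so. Post is tried on all participants and is supported by a text alert and reminders. Calls are tried, at the researcher's discretion, on those for whom post has not produced data. Two routes that work equally well per person approached would then show different shares, simply because one comes first.

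At stake is the usefulness of one feasibility output. Section 8 says that detail on appropriate data collection methods will inform the confirmatory trial, and section 7.2 makes the feasibility of obtaining CORE-OM, that trial's primary outcome, an objective. A table of shares presented as evidence on the best method could be over-read when follow-up for that trial is planned.

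**Working it through.** **Stated figure near this point.** The protocol gives no response rate by route. The nearest figure is the interval around the 75% follow-up criterion in Table 2 of section 17.1. With n = 30: 0.75 ± 1.96 × √(0.75 × 0.25 / 30) = 0.75 ± 0.155, or 59.5% to 90.5%. This matches the protocol. It concerns overall completion and does not depend on the route.

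**Inputs.**
- n = 30 (section 17.1), all registered participants in the denominator (section 17.3).
- Post to all; calls only to those who do not return by post (sections 12 and 12.3).
- p = probability that post succeeds, q = probability that a call succeeds in a postal non-responder. Both are assumptions, and a range is shown.
- For simplicity, every postal non-responder is called. Online is left out because it has no described place in the order.

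**Formulas.** Expected postal count = 30p. Expected call count = 30(1 − p)q. Total completion = p + (1 − p)q. Calls lead in expectation only if (1 − p)q > p, that is, q > p/(1 − p). At p = 0.5 the right-hand side is 1, so from there on calls cannot lead in expectation, however well they work. The last two columns are exact binomial probabilities that one count exceeds the other; the remainder is the chance of a tie.

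| p | q | Post | Calls | Total | P(post ahead) | P(calls ahead) |
|---|---|---|---|---|---|---|
| 0.3 | 0.3 | 9.0 | 6.3 | 51% | 0.715 | 0.205 |
| 0.4 | 0.4 | 12.0 | 7.2 | 64% | 0.841 | 0.110 |
| 0.5 | 0.5 | 15.0 | 7.5 | 75% | 0.936 | 0.041 |
| 0.6 | 0.6 | 18.0 | 7.2 | 84% | 0.985 | 0.009 |
| 0.7 | 0.7 | 21.0 | 6.3 | 91% | 0.998 | 0.001 |
| 0.4 | 0.6 | 12.0 | 10.8 | 76% | 0.559 | 0.361 |
| 0.5 | 0.9 | 15.0 | 13.5 | 95% | 0.574 | 0.352 |
| 0.3 | 0.5 | 9.0 | 10.5 | 65% | 0.325 | 0.590 |
| 0.2 | 0.4 | 6.0 | 9.6 | 52% | 0.146 | 0.787 |

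**Reading the table.** In the first five rows the two routes succeed equally often per person approached, yet post is expected to show the larger share. At 50% each, the planned summary shows 15/30 = 50% for post and 7.5/30 = 25% for calls, while success per person approached is 15/30 and 7.5/15, both 50%. The last two rows show the order reversing when postal return is low. The same measure can thus point either way, depending on p and on who was contacted first.

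**The case against.** **The sequence is not settled throughout.** Sections 3, 7.2, 8 and 15 list the routes side by side, and online has no step. This stands as a limit: the argument is clearest for post against telephone, video or face-to-face contact. It does not remove the point, because sections 12 and 12.3 and Table 1, which describe how the data are collected, put post first.

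**No ranking rule is stated, and layout belongs in the SAP.** Section 17.3.2 is descriptive, does not say that the largest share wins, and section 17.2 defers detail to a later plan. Step-level tables would indeed be ordinary SAP content. But the protocol itself ties the best-method question to this measure, and that pairing is the problem.

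**Little information is lost.** If post goes to all 30, the number left for calls is roughly 30 minus the postal returns. This is partly right, but section 12.3 makes calls optional, so the number actually attempted cannot be recovered from the shares without a log.

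**Yield per attempt depends on order too.** This stands fully. Success by telephone among people who ignored a postal pack and reminders does not show how telephone would do if used first. It can be reported as the increment of a sequence, not as a comparison of methods.

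**The consequence is small.** The Table 2 follow-up criterion counts completion by any route. Section 16 interviews also inform follow-up procedures, and section 17.3.2 adds completion rates, time spent and reported acceptability of the questionnaires. This stands and sets the severity.

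A reader might go further and infer that post must come out ahead, or that the plan will rank the methods wrongly and telephone is the better one. The documents do not support this. With 40% and 60% assumed, post is ahead with probability only 0.559; at low postal return calls lead; and nothing in the design shows which method would do better if used first.

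**Conclusion.** The point holds in a limited form and is minor. Under a post-first scheme, the share of data by route mixes how well a route works with when it was used, so it cannot identify a best method. The distortion may be large (15 against 7.5 of 30 for two routes equally effective at an assumed 50%) or run the other way (6.0 against 9.6 at an assumed 20% and 40%). These sizes rest on assumed response rates, on every postal non-responder being called, and on the order in sections 12 and 12.3 being the one followed.

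What is affected is a descriptive output that informs data collection in the definitive trial. Overall completion, the number of participants added by calls, and the follow-up progression criterion remain valid as planned.

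**What to change.** In sections 15 and 17.3.2, replace the best-method assessment with a description of the sequential collection strategy. For each step (post, first reminder, second reminder, telephone or video call, face to face), report:
- the number attempted;
- the number completed;
- the incremental yield, completed over attempted, with 95% CI;
- cumulative completion out of all registered participants.

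State that yield at a later step applies only to those who had not responded before it, and is not a head-to-head comparison of methods. State where online completion sits in the sequence, and bring the lists of routes in sections 3, 7.2, 8, 12, 12.3 and 15 into line.

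The cost is protocol and SAP wording plus a contact log that records attempts as well as successes from the start. No extra participants are needed. The downside is wide step-level intervals: at 50% yield in 15 people called, the half-width is 1.96 × √(0.25 / 15) = 0.253, or about 25% to 75%, so these figures should be read as description only.

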18. TRIAL MONITORING

A Monitoring Plan will be developed and agreed by the Trial Management Group (TMG) and PSC based on the trial risk assessment; this may include on site monitoring.

18.1. Programme Steering Committee (PSC)

The PSC will provide overall supervision of the study - in particular, study progress, adherence to protocol, participant safety, and consideration of new information. The committee will meet once during the set-up period and at least annually thereafter for the duration of the study. A subcommittee of the PSC will be convened where necessary to monitor safety data.

18.2. Data Monitoring

Data will be monitored for quality and completeness by the CTRU. Missing data will be chased until it is received, confirmed as not available or the study is at analysis. However missing data items will not be chased from participants (although missing questionnaires will be where appropriate). The CTRU/Sponsor will reserve the right to intermittently conduct source data verification exercises on a sample of participants, which will be carried out by staff from the CTRU/Sponsor. Source data verification will involve direct access to patient notes at the participating hospital sites and the ongoing central collection of copies of consent forms and other relevant investigation reports.

18.3. Clinical Governance Issues

To ensure responsibility and accountability for the overall quality of care received by participants during the study period, clinical governance issues pertaining to all aspects of routine management will be brought to the attention of the PSC and, where applicable, to individual NHS Trusts.

19. QUALITY ASSURANCE AND ETHICAL CONSIDERATIONS

19.1. Quality assurance

The study will be conducted in accordance with current MRC Good Clinical Practice (GCP) guidelines, UK Policy Framework for Health and Social Care Research 2017 and complies with the Mental Capacity Act (2005), through adherence to CTRU standard operating procedures (SOPs) and relevant study-specific SOPs.

19.2. Serious Breaches

Investigators are required to promptly notify the CTRU of a serious breach (as defined in the latest version of the National Research Ethics Service (NRES) SOP). A 'serious breach' is defined as a breach of the protocol or of the conditions or principles of GCP (or equivalent standards for conduct of non-CTIMPs) which is likely to affect to a significant degree the safety or physical or mental integrity of the trial subjects, or the scientific value of the research.

In the event of doubt or for further information, the Investigator should contact the Trial Manager at the CTRU.

19.3. Ethical considerations

The trial will be performed in accordance with the recommendations guiding physicians in biomedical research involving human subjects adopted by the 18th World Medical Assembly, Helsinki, Finland, 1964, amended at the 52nd World Medical Association General Assembly, Edinburgh, Scotland, and October 2000. The right of the patient to refuse participation without giving reasons must be respected. The patient must remain free to withdraw from the trial at any time without giving reasons and without prejudicing their care or treatment. The trial documentation will be submitted by CTRU to the identified Research Ethics Committee (REC). The trial must be approved by that REC and receive Management approval from each participating site prior to any participants entering the trial.

19.4. Submission of Study Data

Case Report Forms

Data will be recorded by researchers / site staff on trial-specific paper CRFs and submitted by post to the CTRU at the University of Leeds. Only the participant's trial number plus date of birth and initials will be added to CRFs in order to identify the participant. The site / researcher is responsible for obliterating all other personal identifiable data prior to sending CRFs and any other reports to the CTRU (with the exception of the patient consent form which will include the patient's name and signature). Following receipt, the CTRU will contact the trial site to resolve any missing or discrepant data queries.

The CTRU will seek to adopt all reasonable measures to record data in accordance with the protocol. Under practical working conditions some minor variations may occur due to circumstances beyond the control the CTRU. All such deviations will be documented on the study records, together with the reason for their occurrence; where appropriate, deviations will be detailed in the published report.

Interview data

Data collected through observations (field notes and observational records, audio and/or video recorded interviews, summaries of documentary analysis), and reflective reports will be anonymised and stored at LIHS.

